4.5.2 Physical examination

Information about the physical examination must be present in the source documentation at the study site. Significant findings that are present prior to the start of study drug must be included in the Medical History section of the CRF or Current Medical Conditions section of the CRF. Significant findings reported after the start of treatment with the study drug that meet the definition of an AE must be recorded in the Adverse Event section of the CRF.

Study visit schedule and required evaluations and procedures to be performed at each study visit are described below and summarized in the flow-chart in [Appendix A](#). Methods of assessment of safety and efficacy are described in the [paragraph 4.6](#) and [paragraph 4.7](#) of the present protocol.

4.5.3 Spleen evaluation, PK and PD characterization, molecular examinations and bone marrow histological evaluation

4.5.3.1 Spleen evaluation

The spleen evaluation must be performed at the study centre according to the visit schedule outlined in the flow-chart ([Appendix A](#)).

The spleen evaluation will be performed during the study according to institutional guidelines and site-specific clinical practice (i.e. MRI or CT scan). The same imaging technique and the same instrument to assess spleen dimension (i.e. MRI or CT scan) should be used on a patient throughout the study, *if possible*.

If possible, the spleen dimension will be evaluated as longitudinal diameter (hereafter “A”), antero-posterior diameter (hereafter “B”), transversal diameter (hereafter “C”) and Splenic Volumetric Index (hereafter “SVI”):

$$SVI = (A \times B \times C) / 27$$

No spleen evaluation will be performed in splenectomised patients.

4.5.3.2 PK characterization

Approximately 5.0 mL of blood for pharmacokinetic assessment will be collected as following described:

- 1) Day 1 of Cycle 1 of **Parts A** and **B**: before the first Givinostat dose (pre-dose) and 2, 3 and 8 (before the second Givinostat dose) hours after the first drug administration ([Appendix A](#)).

e.g.: the PK pre-dose evaluation will be performed at 7.45 a.m. of Day 1 (pre-dose) of Cycle 1 of **Parts A** and **B** and after that the patient will take the first drug

- administration (e.g. at 8.00 a.m.); then, the patient will perform the PK post-dose evaluations at 10.00 a.m. (hour 2), 11.00 a.m. (hour 3) and at 16.00 p.m. (hour 8).
- 2) Day 28 of the Cycle 1 of **Part A**: before the first daily Givinostat dose (pre-dose) and 1, 2, 4 and 8 (before the second Givinostat dose) after the first daily drug administration ([Appendix A](#)).
- e.g.: the PK pre-dose evaluation will be performed at 7.45 a.m. of Day 28 of Cycle 1 (pre-dose) of **Part A** and after that the patient will take the first daily drug administration (e.g. at 8.00 a.m.); then, the patient will perform the PK post-dose evaluations at 9.00 a.m. (hour 1), 10.00 a.m. (hour 2), 12.00 p.m. (hour 4) and at 16.00 p.m. (hour 8).
- 3) Day 28 of the Cycles 2, 3, 4, 5, and 6 of **Part A**: before the first daily Givinostat dose (pre-dose) ([Appendix A](#)).
- e.g.: the PK pre-dose evaluation will be performed at 7.45 a.m. of Day 28 of Cycle 2 and beyond Cycles (i.e. Cycles 3, 4, 5 and 6) of **Part A** (pre-dose) and after that the patient will take the first daily drug administration (e.g. at 8.00 a.m.).
- 4) Day 28 of Cycle 2 of **Part B**: before the first daily Givinostat dose (pre-dose) and 1, 2, 4 and 8 (before the second Givinostat dose) hours after the first daily drug administration ([Appendix A](#)).
- e.g.: the PK pre-dose evaluation will be performed at 7.45 a.m. of Day 28 of Cycle 2 (pre-dose) of **Part B** and after that the patient will take the first daily drug administration (e.g. at 8.00 a.m.); then, the patient will perform the PK post-dose evaluations at 9.00 a.m. (hour 1), 10.00 a.m. (hour 2), 12.00 a.m. (hour 4) and at 16.00 p.m. (hour 8).

The PK samples should be drawn as closely to the predefined time as possible.

The exact timing of PK sampling could be adjusted based on emerging clinical and preclinical data.

For all time points an additional PK blood sample will be collected as back-up sample.

This assessment is mandatory and will be performed by a central laboratory. The exact date and time of the PK blood draws will be recorded along with the date and time of the last dose of study drug preceding the blood draw. Additional information about the PK time points, instructions for sample preparation and shipment will be provided in the related study handling manual.

After evaluation of preliminary results and data exploration, some additional analyses may be performed to identify and quantify other molecular parameters of interest in term of improving of the knowledge of cMPN and the activity of the drug in these disorders.

4.5.3.3 PD characterization

Approximately 4.0 mL of blood for pharmacodynamic markers will be collected before the first Givinostat dose (pre-dose) and 12 hours after the first Givinostat dose (post-dose) at Day 1 of Cycle 1 both in **Part A** and in **Part B** for measurement of levels of

molecular markers, to evaluate the pharmacodynamic effect of Givinostat and to identify markers predictive of clinical benefit of Givinostat ([Appendix A](#)). In addition, pharmacodynamic evaluations will be performed also using an aliquot of the PK samples collected at time points described in the [paragraph 4.5.3.2](#) [34]. The molecular markers to be measured may include mRNA levels of JAK2, STAT5A, BclXL, PIM1, NFE2, LMO2, cMyc as well as HDAC3, STAT4, MYBL1, MEGF9, GLRX, FAM49A. The final list of pharmacodynamic markers to be measured will depend on ongoing scientific developments as well as availability of assays and other business considerations.

For all time points an additional PD blood sample will be collected as back-up sample.

This assessment is mandatory and will be performed by a central laboratory. The exact date and time of the PD blood draws will be recorded along with the date and time of the last dose of study drug preceding the blood draw. Instructions for sample preparation and shipment will be provided in a separate and specific laboratory manual.

After evaluation of preliminary results and data exploration, some additional analyses may be performed to identify and quantify other molecular parameters of interest in term of improving of the knowledge of cMPN and the activity of the drug in these disorders.

4.5.3.4 JAK2^{V617F} characterization

JAK2^{V617F} characterization (i.e. JAK2^{V617F} allele burden evaluated by quantitative RT-PCR) will be performed in a central laboratory ([Appendix E](#)). Detailed instructions for sample preparation and shipment will be provided in a separate and specific laboratory manual.

For all time points a blood sample will be collected as back-up sample.

After evaluation of preliminary results and data exploration, some additional analyses may be performed to identify and quantify other molecular parameters of interest in term of improving of the knowledge of cMPN and the activity of the drug in these disorders.

4.5.3.5 Molecular examinations

All molecular examinations (e.g. JAK2^{V617F} allele burden evaluated by quantitative RT-PCR, mRNA isolation, gene expression) will be performed in a central laboratory.

Detailed instructions for sample preparation and shipment will be provided in a separate and specific laboratory manual.

The results will be transcribed into the CRF by the central laboratory team or its designee and the original signed and dated laboratory print-out/tracings will be monitored and stored at the central laboratory.

After evaluation of preliminary results and data exploration, some additional analyses may be performed to identify and quantify other molecular parameters of interest in

term of improving of the knowledge of cMPN and the activity of the drug in these disorders.

4.5.3.6 Bone marrow histological evaluation

A bone marrow histological evaluation will be performed to all patients recruited in **Part B** in order to assess the presence of age adjusted normocellularity and/or trilinear hyperplasia as requested by the “new” ELN response criteria (i.e. the **revised** ELN response criteria) [33] (see [paragraph 4.8.7](#)).

This examination will be performed in the local laboratory of each site. The results of this test will be transcribed into the CRF and the original signed and dated laboratory print-out/tracings, including the assessment of the presence of age adjusted normocellularity and/or trilinear hyperplasia, will be monitored and stored at the study site.

Please note that, in case the patient performs the bone marrow histological evaluation as requested by the “new” ELN criteria (i.e. the **revised** ELN response criteria) [33] (see [paragraph 4.8.7](#)) – i.e. bone marrow evolution including the assessment of the presence of age adjusted normocellularity and/or trilinear hyperplasia - 1 month before the study start (i.e. the signature of the Informed Consent Form), this examination has not to be repeated for this study in order to limit the discomfort for the patient. In any case, the results of this test will be transcribed into the CRF and the original signed and dated laboratory print-out/tracings, including the assessment of the presence of age adjusted normocellularity and/or trilinear hyperplasia, will be monitored and stored at the study site.

In case the patient drops-out the study during the first 3 Cycles (i.e. before the Day 28 of Cycle 3), this evaluation has not to be performed at End of Study visit.

Finally, in case the patient refuses to provide this written consent to perform the bone marrow evaluation, this patient can be anyway recruited in **Part B**. However, this patient will not be counted to assess the related exploratory endpoints (i.e. overall response rate of Givinostat at the MTD after 6 cycles according to the **revised** ELN response criteria [33], and the evaluation of the effect of Givinostat on each single response parameter according to the **revised** ELN response criteria [33]).

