Please note that, in case the patient performs the bone marrow histological evaluation as requested by the “new” ELN criteria (i.e. the **revised** ELN response criteria) [33] (see [paragraph 4.8.7](#)) – i.e. bone marrow evolution including the assessment of the presence of age adjusted normocellularity and/or trilinear hyperplasia - 1 month before the study start (i.e. the signature of the Informed Consent Form), this examination has not to be repeated for this study in order to limit the discomfort for the patient. In any case, the results of this test will be transcribed into the CRF and the original signed and dated laboratory print-out/tracings, including the assessment of the presence of age adjusted normocellularity and/or trilinear hyperplasia, will be monitored and stored at the study site.

In case the patient refuses to provide this written consent to perform the bone marrow evaluation, this patient can be anyway recruited in **Part B**. However, this patient will not be counted to assess the related exploratory endpoints (i.e. overall response rate of Givinostat at the MTD after 6 cycles according to the revised ELN response criteria [33], and the evaluation of the effect of Givinostat on each single response parameter according to the revised ELN response criteria [33]).

If all eligibility criteria are met at the pre-treatment visit, the treatment with Givinostat can start.

After the check that all eligibility criteria are met by the patient and in any case before the treatment start, all patients with an uncontrolled HCT (i.e. HCT $\geq 45\%$) have to perform phlebotomy(ies) to normalize the HCT value (i.e. HCT $<45\%$).

In case of patients who are phlebotomy-dependent, all efforts have to be made by Investigators to record all phlebotomies with recruited patients experienced at least 6 months before the treatment start.

4.5.4.2.2 Day 1 of Cycle 1

The following procedures must be performed exactly at Day 1 of Cycle 1 of **Part B** as reported below:

1) Pre-dose evaluations:

The following procedures will be performed **before the first Givinostat dose** as reported below:

- Adverse event recording;
- Concomitant medications (drugs);
- Significant non-drug therapies (e.g. phlebotomies, transfusions) recording (*if applicable*);
- PD sample collection;
- PK sample collection and preparation, in order to allow to perform both the PK and PD evaluations starting from the same sample [34] (*if requested*).

2) Post-dose evaluations:

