4.8.7 Evaluation of preliminary efficacy according to the revised ELN criteria

Disease response will be evaluated also according to the following “**new**” ELN criteria (i.e. the **revised** ELN response criteria) **after 6 cycles** of treatment with Givinostat in **Part B** [33].

- **Complete remission:**
 1. *Durable* resolution of disease-related signs including palpable hepatosplenomegaly improvement, and *large symptoms improvement*, **and**
 2. *Durable* peripheral blood count remission, defined as HCT < 45% without phlebotomies, and PLT count $\leq 400 \times 10^9/L$, and WBC count < $10 \times 10^9/L$, **and**
 3. No progressive disease, and absence of any hemorrhagic or thrombotic event, **and**
 4. Bone marrow histological remission defined as the presence of age-adjusted normo-cellularity, and disappearance of tri-linear hyperplasia, and absence of grade > 1 reticulin fibrosis.
- **Partial remission:**
 1. *Durable* resolution of disease-related signs including palpable hepatosplenomegaly, and *large symptoms improvement*, **and**
 2. *Durable* peripheral blood count remission, defined as HCT < 45% without phlebotomies, and PLT count $\leq 400 \times 10^9/L$, and WBC count < $10 \times 10^9/L$, **and**
 3. No progressive disease, and absence of any hemorrhagic or thrombotic event, **and**
 4. No bone marrow histological remission defined as persistence of tri-linear hyperplasia.
- **No response:** any response that does not satisfy partial remission.
- **Progressive Disease:** transformation into post-PV myelofibrosis, myelodysplastic syndrome or acute leukemia (according to the IWG-MRT criteria for the diagnosis of post-PV myelofibrosis and according to WHO criteria for the diagnosis of myelodysplastic syndrome and acute leukemia).

Please note that according to the “new” ELN criteria (i.e. **revised** ELN response criteria) [33]:

- 1) Molecular response is not required for assignment as Complete Remission or Partial Remission. Molecular response evaluation requires analysis in peripheral blood granulocytes. Complete response is defined as eradication of a pre-existing abnormality. Partial response applies only to patients with at least 20% mutant allele burden at baseline. Partial response is defined as $\geq 50\%$ decrease in allele burden.
- 2) “*Durable*” is defined as lasting at least 12 weeks.
- 3) “*Large symptom improvement*” is defined as ≥ 10 points of decrease in MPN-SAF Total Symptom Score [32].

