10.1.2 Flow-chart of Part B

	Pre-treatment evaluations *** (up to 4 weeks: -28 to Day -1)	Day 1 of the first Cycle ***		Day 28 of Cycles 1, 2, 4 and 5 ***	Day 28 of Cycles 3 and 6 ***	End of study visit (in case of completed study) or 7 days after last drug intake (in case of the patient drops-out of the study) ^{11,***}
Treatment phase	Pre-dose	Pre-dose	Post-dose	TREATMENT		
Windows	± 7 days	Not applicable		± 3 days		
Visit at the investigational site	X	X	X	X	X	X
Informed Consent Form signature	X					
Demographic data	X					
Adverse event recording	X	X	X	X	X	X
Concomitant medications (drugs)	X	X	X	X	X	X
Non-drug therapies (e.g. phlebotomies, transfusions)	X	X	X	X	X	X
Medical history	X					
Physical examination, vital signs (blood pressure, pulse rate, respiratory rate), height, weight, body temperature and ECOG performance status ¹	X			X	X	X
Pregnancy test (if indicated) ²	X					
Blood chemistry ³	X			X	X	X
ECG, QTc determination (according with Bazett's correction formula) ¹²	X			X	X	X
Urinalysis ⁴	X					
Haematology ⁵	X			X	X	X
PD sample collection before the first Givinostat dose *		X				
PD sample collection 12 hours after the first Givinostat dose *			X			
PK sample collection ^{6,*} and preparation, in order to allow to perform both the PK and PD evaluations starting from the same sample (if requested)		X	X	X		

	Pre-treatment evaluations (up to 4 weeks: -28 to Day -1) ^{***}	Day 1 of the first Cycle ^{***}		Day 28 of Cycles 1, 2, 4 and 5	Day 28 of Cycles 3 and 6	End of study visit (in case of completed study) or 7 days after last drug intake (in case of the patient drops-out of the study) ¹¹
Treatment phase	Pre-dose	Pre-dose	Post-dose	TREATMENT		
Windows	± 7 days	Not applicable		± 3 days		
Visit at the investigational site	X	X	X	X	X	X
Spleen evaluation (by MRI or CT scan) ⁷	X				X	X
Collection of blood sample for quantitative RT-PCR evaluation of JAK2 ^{V617F} mutational status on peripheral blood (PB) granulocyte [*]	X			X	X	X
Assessment of disease-related symptoms using the MPN-SAF QOL Questionnaire [24, 32]	X				X	X
Bone marrow histological evaluation in order to assess the presence of age adjusted normocellularity and/or trilinear hyperplasia ^A	X				X ^B	X ^C
Therapeutic response evaluation ⁸					X	X
Request of enrolment and receipt of patient ID	X					
Givinostat administration ⁹				X	X ^{**}	
First Givinostat dose and accountability			X			

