^A Please note that, in case the patient performs the bone marrow histological evaluation as requested by the “new” ELN criteria (i.e. the **revised** ELN response criteria) [33] (see [paragraph 4.8.7](#)) – i.e. bone marrow evolution including the assessment of the presence of age adjusted normocellularity and/or trilinear hyperplasia - 1 month before the study start (i.e. the signature of the Informed Consent Form), this examination has not to be repeated for this study in order to limit the discomfort for the patient. In any case, the results of this test will be transcribed into the CRF and the original signed and dated laboratory print-out/tracings, including the assessment of the presence of age adjusted normocellularity and/or trilinear hyperplasia, will be monitored and stored at the study site.

Finally, in case the patient refuses to provide this written consent to perform the bone marrow evaluation, this patient can be anyway recruited in **Part B**. However, this patient will not be counted to assess the related exploratory endpoints (i.e. overall response rate of Givinostat at the MTD after 6 cycles according to the revised ELN response criteria [33], and the evaluation of the effect of Givinostat on each single response parameter according to the revised ELN response criteria [33]).

^B Only for *cycle 6*.

^C In case the patient drops-out the study during the first 3 Cycles (i.e. before the Day 28 of Cycle 3) , this evaluation has not to be performed at End of Study visit.

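### Part B marrow procedures do not require the reticulin fibrosis grade that Complete Remission under the revised ELN criteria depends on (exploratory endpoint)

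*Protocol*

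**What the plan says.** Section 4.8.7 (repeated in the synopsis, Criteria for Response) sets three joint marrow conditions for Complete Remission: age-adjusted normocellularity, "disappearance of tri-linear hyperplasia, and absence of grade > 1 reticulin fibrosis". The marrow condition for Partial Remission is "No bone marrow histological remission defined as persistence of tri-linear hyperplasia". No response is "any response that does not satisfy partial remission".

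The content of the Part B marrow examination is described in four places, and each names two features only:

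- Section 4.5.3.6, purpose: "in order to assess the presence of age adjusted normocellularity and/or trilinear hyperplasia as requested by the" revised criteria. The report kept at the site is described as "including the assessment of the presence of age adjusted normocellularity and/or trilinear hyperplasia, will be monitored and stored at the study site".
- Section 4.5.4.2.1, on accepting a marrow from the month before consent in place of the baseline sample: "bone marrow evolution including the assessment of the presence of age adjusted normocellularity and/or trilinear hyperplasia".
- Section 10.1.2, flow-chart row: "Bone marrow histological evaluation in order to assess the presence of age adjusted normocellularity and/or trilinear hyperplasia".
- Section 10.1.2, footnote A: "including the assessment of the presence of age adjusted normocellularity and/or trilinear hyperplasia".

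The visit lists for Cycle 6 (4.5.4.2.4) and End of Study (4.5.4.2.5) schedule the examination without stating its content. They also call for a response evaluation under 4.8.7.

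**The concern.** The response definition needs an item that the procedure text does not ask for. The procedure text also presents its shorter list as what the revised criteria request. A local laboratory that follows it can return a report with no fibrosis grade. Because of *and/or*, the report might even cover only one of the two named features.

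Two exploratory Part B endpoints in section 3.3 are at stake: the revised ELN response rate after 6 cycles, and the effect on each single parameter of those criteria. Patients undergo an optional invasive procedure for these endpoints, so the sample should yield what the definition needs. A statistical analysis plan can set a missing-data rule, but it cannot supply an item that was never collected. The protocol provides back-up samples for the blood assays but states no retention of marrow tissue for later grading.

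**Working it through.** The protocol states no figure on this point, so there is none to reproduce. The check applies the 4.8.7 definitions to every possible marrow result.

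**Inputs.** Three yes/no marrow features, with all non-marrow conditions of 4.8.7 taken as met. Literal rules: Complete Remission (CR) if the marrow is normocellular, trilinear hyperplasia has gone and fibrosis is not above grade 1; Partial Remission (PR) if trilinear hyperplasia persists; otherwise No response (NR). The last column assumes that an unrecorded grade is read as no fibrosis above grade 1.

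| Normocellular | Trilinear hyperplasia persists | Reticulin grade > 1 | Grade recorded | Grade unrecorded, taken as absent |
|---|---|---|---|---|
| yes | no | no | CR | CR |
| yes | no | yes | **NR** | **CR** |
| yes | yes | no | PR | PR |
| yes | yes | yes | PR | PR |
| no | no | no | NR | NR |
| no | no | yes | NR | NR |
| no | yes | no | PR | PR |
| no | yes | yes | PR | PR |

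**Result.** One of the eight patterns changes class. It moves from No response to Complete Remission because Partial Remission, read literally, needs persistent hyperplasia, so a patient who fails Complete Remission on fibrosis alone does not drop into Partial Remission. The error can only raise the response rate.

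**Without the assumption.** If a missing grade is not read as absence, the first two rows cannot be told apart. A patient with a normocellular marrow and no hyperplasia then cannot be assigned Complete Remission, even if it was truly achieved.

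**Effect of *and/or*.** If a report covered cellularity alone, neither Complete nor Partial Remission could be assigned, because both depend on hyperplasia.

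**Size per patient.** Part B plans up to 28 patients. If all have an evaluable marrow, one misclassified patient moves the rate by 1/28 = 3.6 percentage points. Patients who refuse the marrow are not counted for this endpoint (4.5.3.6), so the denominator may be smaller. With 14 evaluable marrows, an assumed figure, it is 1/14 = 7.1 points. The protocol gives no frequency for fibrosis above grade 1, so an expected total bias cannot be calculated.

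**The case against.** A reader might infer that fibrosis will not be measured at all. The text does not support that. Sections 4.5.3.6 and 4.5.4.2.1 and footnote A use *including*, which is not exhaustive, and refer to 4.8.7, where the grade appears. The visit lists require a response evaluation under 4.8.7, and section 4.8.8 says every single parameter of the criteria will be used. The sentence in 4.5.3.6 on entering results in the CRF is not limited to two items, and the CRF itself is not at hand. A careful site could well grade fibrosis. What stands is that no procedure text requires it, and the stated purpose in 4.5.3.6 and the flow-chart row carries no *including*.

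A reader might also infer that false Complete Remissions will follow. That needs a missing grade to be treated as absence, which no section says. Sections 6.2.5.2 and 6.2.6.2, written for the primary and secondary endpoints, leave other missing data unreplaced unless otherwise specified. Crossing the responder line further needs the literal reading of Partial Remission. If its opening words, that there is no marrow remission, are taken to govern, the fibrotic patient is a partial responder; only the Complete Remission call would then be wrong, not the overall rate.

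The *and/or* can be read as listing possible findings rather than as permission to report only one. That reading is fair, but the wording leaves the matter open.

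Finally, a reader might take the 3.6 points to concern the primary response rate. They do not: the primary and secondary endpoints use the clinico-haematological criteria in 4.6.1, which have no marrow item.

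**Conclusion.** The mismatch between 4.8.7 and the marrow procedure text is real. The fibrosis grade is not required to be read or recorded, so Complete Remission under the revised criteria may not be determinable as defined. The consequence is confined to exploratory, descriptively analysed Part B endpoints in patients who consent to marrow sampling. The primary and secondary response endpoints, the Simon two-stage rule and the sample size are untouched.

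The change from No response to Complete Remission is conditional on two things: an unrecorded grade being treated as absence, and the literal reading of Partial Remission. Under those conditions each affected patient adds at least 3.6 percentage points to the exploratory rate, and the number of such patients is unknown. The gap in what must be collected depends on neither condition.

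**What to change.** In 4.5.3.6, 4.5.4.2.1, the Part B flow-chart row and footnote A, replace *and/or* with *and*, and name reticulin fibrosis grade as a required item alongside cellularity and trilinear hyperplasia, recorded at Cycle 6 / End of Study whenever a marrow is taken. Record the grade at baseline where it is available, but do not require a repeat biopsy when an otherwise acceptable pre-study marrow lacks it: the fibrosis criterion is judged on the post-treatment marrow, and the protocol aims to spare patients a second sample.

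In 4.8.7, state how a marrow with no trilinear hyperplasia but fibrosis above grade 1 is classed, and state that a missing grade does not count as absence of fibrosis.

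The cost is wording, plus a CRF field if the form does not already have one. The grade is read on the same sample, so no additional biopsy is needed.
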